## 1. BACKGROUND AND RATIONALE

People of lower socioeconomic position (SEP) are more likely to have obesity than people of higher SEP and SEP inequities in obesity in Europe are widening [1]. Lower socioeconomic position (SEP) is associated with a more energy dense diet [2], [3]. Consumption of more energy dense foods has been consistently linked to higher energy intake in experimental studies [4] and results from prospective cohort studies have shown a positive association between energy density (ED) of the total diet and BMI [4]. Thus, the association between SEP and obesity may be mediated, in part, by the consumption of a more energy-dense diet [5]. Interventions that reduce dietary energy density would benefit public health, particularly among people of lower SEP.

In the UK, 26% of the adults eat meals out one or more times per week and 20% eat takeaway meals at home one or more times per week, suggesting that the major part of the meals consists in food prepared at home [6]. People from lower SEP tend to spend a greater proportion of their average food expenditure on prepared-at-home produce (such as products purchased in supermarkets) as opposed to catering services than people of higher SEP (lowest equivalised disposable income decile group: 74% vs. highest: 60%) [7]. Thus, nutrition interventions targeting supermarket purchases provide an opportunity to benefit the diet of all of the population and people of lower SEP in particular.

Information-based nutrition interventions are one of the most common approaches to improving diet [8], [9]. An example of an information-based intervention is menu energy labelling in restaurants [10]. This type of interventions has been suggested to be less effective among people of lower compared to higher SEP [11], [12]. However, systematic reviews of the impact of menu energy labelling has highlighted the limited quality of evidence supporting this hypothesis [11], [13]. It has been suggested that structural interventions that target core features of the food environment (i.e., reducing portion sizes, increasing the availability of healthier food options) and require individuals to use a low level of agency may be most effective and most equitable [8], [14], [15]. However, there is a lack of empirical evidence to support this hypothesis.

Information-based interventions typically rely on people being motivated by health in their food choices [16]. Yet, health may be a less influential motive for food choice among people of lower SEP [17]. Thus, SEP based differences in food choice motives, and notably health motivation, may explain why information-based interventions could be less effective among people of lower vs. higher SEP.

The aim of this study is to examine how an information-based intervention (labelling of lower ED food products) and a structural intervention (greater proportion of lower ED options in food product ranges) affect the ED of food purchases within a virtual online supermarket [18] in participants of lower vs. higher SEP. The primary hypothesis is that labelling will reduce the ED of virtual online supermarket food purchases to a greater extent in participants of higher SEP vs. lower SEP. Conversely, we hypothesise that a greater proportion of lower ED options will decrease the ED of food purchases equally among participants of lower and higher SEP. The secondary hypothesis is that differences in health-based food choice motives in participants of lower vs. higher SEP will mediate the differential effect that ED labelling has on ED of food purchases among participants of lower vs. higher SEP.

## 2. OBJECTIVES, OUTCOMES MEASURES AND HYPOTHESES

OBJECTIVES	OUTCOME MEASURES	HYPOTHESES
Primary objective		

To examine the effectiveness of an information-based intervention (ED labelling) and a structural nutrition intervention (greater proportion of lower ED options) on the ED of virtual online supermarket food purchases; and if this effect is different between participants of lower and higher SEP.	Mean ED (kcal/100g) of foods purchased	SEP will influence the effect of the interventions. In particular, ED labelling will reduce ED of foods purchased to a greater extent in participants of higher vs. lower SEP. Conversely, a greater proportion of lower ED options will decrease ED of food purchases equally among participants of lower and higher SEP.
Secondary objectives  To investigate the psychological processes that explain why an information-based intervention (ED labelling) and a structural nutrition intervention (greater proportion of lower ED options) may have differential effects on ED of food purchases among participants of lower vs. higher SEP.	Health and weight control food choices motives (questionnaire score)	The participants of higher SEP will be more motivated by health and weight control in their food choices than participants of lower SEP, which will moderate the relationship between SEP and the effect of ED labelling on ED of foods purchased.

### 3. EXPERIMENTAL DESIGN

This study will be a 2x2 randomised controlled trial with information-based intervention (no labelling / labelling) and structural intervention (default proportion / increased proportion of lower ED food items) as between-subject factors and ED (kcal/g) of food purchases during an online supermarket-shopping task as dependent variable.

### 4. PARTICIPANTS AND RECRUITMENT

#### 4.1. Recruitment

Participants will be recruited through an online recruitment panel (Prolific) in which participants are compensated proportionate to the time it takes to complete the online study ( $\approx$  £5/hour reward participants).

Participants' recruitment will be stratified by gender (50% male, 50% female), student status (3.5% yes and 96.5% no) [19] and qualification levels; the proportion of low (below level 4) versus high (level 4 or above) qualification levels will be based on current population statistics from the Labour Force Survey (LFS) 2013 for adults aged 19-64 in England [20]:

- **60% lower qualification levels**
  - No formal qualifications
  - 1–3 GCSEs or equivalent

*(Level 1: first certificate; GCSE - grades 3, 2, 1 or grades D, E, F, G; level 1 award; level 1 certificate; level 1 diploma; level 1 ESOL; level 1 essential skills; level 1 functional skills; level 1 national vocational qualification (NVQ); music grades 1, 2 and 3)*

- 4+ GCSEs or equivalent

*(Level 2: CSE - grade 1; GCSE - grades 9, 8, 7, 6, 5, 4 or grades A\*, A, B, C; intermediate apprenticeship; level 2 award; level 2 certificate; level 2 diploma; level 2 ESOL; level 2 essential skills; level 2 functional skills; level 2 national certificate; level 2 national diploma, level 2 NVQ; music grades 4 and 5; O level - grade A, B or C)*

- A level or equivalent

*(Level 3: A level; access to higher education diploma; advanced apprenticeship; applied general; AS level; international Baccalaureate diploma; level 3 award; level 3 certificate; level 3 diploma; level 3 ESOL; level 3 national certificate; level 3 national diploma; level 3 NVQ; music grades 6, 7 and 8; tech level)*

- **40% higher qualification levels**

- Certificate of higher education (CertHE) or equivalent

*(Level 4: certificate of higher education (CertHE); higher apprenticeship; higher national certificate (HNC); level 4 award; level 4 certificate; level 4 diploma; level 4 NVQ);*

- Diploma of higher education (DipHE) or equivalent

*(Level 5: diploma of higher education (DipHE); foundation degree; higher national diploma (HND); level 5 award; level 5 certificate; level 5 diploma; level 5 NVQ)*

- Bachelor or equivalent

*(Level 6: degree apprenticeship; degree with honours - for example bachelor of the arts (BA) honours, bachelor of science (BSc) honours; graduate certificate; graduate diploma; level 6 award; level 6 certificate; level 6 diploma; level 6 NVQ; ordinary degree without honours)*

- Master's degree or equivalent

*(Level 7: integrated master's degree, for example master of engineering (MEng); level 7 award; level 7 certificate; level 7 diploma; level 7 NVQ; master's degree, for example master of arts (MA), master of science (MSc); postgraduate certificate; postgraduate certificate in education (PGCE); postgraduate diploma)*

- Doctorate or equivalent

*(Level 8: doctorate, for example doctor of philosophy (PhD or DPhil); level 8 award; level 8 certificate; level 8 diploma)*

**4.2. Inclusion criteria**

- UK residents, aged  $\geq 18$  years
- Fluent in English
- Have access to a computer and Internet
- Responsible for a substantial proportion of household grocery shopping

**4.3. Exclusion criteria**

- Unable to provide informed consent and to comply with the study requirements
- Any of the following dietary restrictions:
  - Vegetarian
  - Vegan
  - Gluten-free
  - Sugar-free
  - Dairy/lactose-free

- Food allergy (e.g. milk, eggs, nut, wheat, fish, etc.)

## 5. METHODS

### 5.1. Online shopping task

#### Experimental online supermarket

This study will use an online supermarket platform ([www.woodssupermarket.co.uk](http://www.woodssupermarket.co.uk)) developed to mimic an online supermarket website [18]. As prior work has suggested it is inappropriate to combine food and drinks when calculating ED [21], all the drinks will be removed from the online supermarket.

#### Shopping task

Participants will be asked to complete a shopping task using a pre-determined shopping list of 10 items (**Table 1**).

**Table 1.** Description of the food shopping list.

Food items	Department	Aisle	Shelf	Number of products	Mean ED (min-max)
A packet of biscuits	Food Cupboard	Biscuits & crackers	Biscuits	247	478 (341-574)
A standard sized loaf of bread	Bakery	Bread		142	251 (186-345)
A chilled pizza	Dairy, eggs & chilled	Pizza, pasta & garlic bread	Pizza	24	269 (221-319)
An ice cream tub	Frozen	Ice cream & ice	Ice cream tubs	142	225 (76-341)
A chilled ready meal for one	Dairy, eggs & chilled	Ready meals	Meals for one	185	145 (71-316)
A pack of sausages	Meat & fish	Bacon & sausages	Sausages	53	263 (145-473)
A sharing bag of crisps or savoury snacks	Food Cupboard	Crisps, nuts & snacking fruit	Sharing crisps	144	490 (397-580)
A pre-packed piece of cheese	Dairy, eggs & chilled	Dairy & eggs	Cheese	334	321 (59-527)
A pack of yogurts	Dairy, eggs & chilled	Dairy & eggs	Yogurts	251	87 (39-193)
A jar of jam or sweet spread	Food Cupboard	Jams, honey & spreads	Excluding 'Savoury pastes' and 'Marmite & yeast extracts	156	392 (139-650)

These categories were chosen as representing major contributors to UK diet [22] and because in each category there are products with a range of EDs.

## Interventions

Participants will be randomly allocated to one of the following groups:

- default proportion & no labelling (D);
- default proportion & labelling (DL);
- increased proportion of lower ED food items & no labelling (I);
- increased proportion of lower-ED food items & labelling (IL).

The interventions will only be applied in the aisles and shelves of the online supermarket that include food items from the shopping list. Lower ED products will be defined in relation to a threshold for each aisle or shelf:  $\text{lower ED} \leq \text{median of ED distribution within a food category}$ .

In the *labelling* conditions (DL and IL) “healthier choice” badges will be added to the food item pictures when the above criterion is met. For *labelling* conditions only, instructions when logging-into the platform will introduce the badges to the participants: “In the online supermarket, the green tick allows you to see which products (e.g. muesli) in each product category (e.g. cereals) are healthier choices with fewer calories per gram than most other products in the same category.” The design of the badge is based on previous research investigating the effect of front-of-package nutrition labelling on food choices [23] (**Figure 1**).

**Figure 1.** Healthier choice badge display in the labelling conditions when  $\text{lower ED} \leq \text{median of ED distribution within a food category}$ .

In the *increased proportion* of lower ED food items conditions (I and IL) the proportion of lower ED vs. higher ED options will be reversed (67% lower ED – 33% higher ED) relative to the *default proportion* conditions (D and DL) (33% lower ED – 67% higher ED) (**Table 2**).

**Table 2.** Food items proportion and “healthy” labelling within a specific food category

	d1	d2	d3	d4	d5	d6	d7	d8	d9	d10
Default proportion No labelling	present	absent	absent	absent	present	absent	present	present	present	present
Default proportion Labelling	present healthy	absent	absent	absent	present healthy	absent	present	present	present	present
Increased proportion No labelling	present	present	present	present	absent	present	absent	absent	absent	present
Increased proportion Labelling	present healthy	present healthy	present healthy	present healthy	absent	present	absent	absent	absent	present

*di: food items in a given food category with ED ≤ ith decile of ED distribution within this food category*

Comments on Table 1:

- *d5 or d6* is absent to create a gap between lower and higher ED options that makes “healthier choice” badges credible;
- *d1 (min) and d10 (max)* remain in all conditions.

### 5.2. Measures of socioeconomic position

Four measures of socioeconomic position will be included. Participants will be asked to report:

- their highest educational qualification;
- their number of years in higher education;
- their after tax household income and their household composition in order to calculate their equivalised disposable income [24];
- their household postcode, which will be linked to the English Index of Multiple Deprivation (IMD) [25] for the purpose of other research;
- a subjective measure of their socioeconomic position using the MacArthur Scale of Subjective Social Status (SSS) [26].

### 5.3. Measure of health and weight control food choice motives

We will use the ‘Health’ and ‘Weight control’ subscales from the Food Choice Questionnaire developed Steptoe et al. 1995 [27].

## 6. STUDY FLOW

RECRUITMENT (Prolific)	
 
▪ Predefined screening questions of Prolific website will be used to target the sample (Appendix A)
 
▪ Participants who will meet the inclusion/exclusion criteria will be e-mailed by Prolific and/or will be offered to complete our study on their Prolific account (Appendix B)
 
▪ Eligible participants who want to take part on the study will click on the start button and be redirected to our study website
 
			
INFORMED CONSENT (Qualtrics)	
 
▪ Participants will read the information sheet (Appendix C)
 
▪ Participants who want to proceed will tick a consent box (Appendix D)
 
▪ Participants will be allowed to contact the investigator via the “Contact researcher” button on Prolific webpage
 
			
BASELINE ASSESSMENTS (Qualtrics)	
 
▪ Participants will complete a baseline questionnaire on demographic, grocery shopping and health data (Appendix E)
 
			
RANDOMISATION (Qualtrics)	
 
▪ Participants will be randomly allocated to one of the four experimental conditions; same number of participants in each of the four groups.
 
			
	Default proportion & no labelling (D)	Default proportion & labelling (DL)	Increased proportion & no labelling (I)	Increased proportion & labelling (IL)
ONLINE SHOPPING TASK (Woods)	
 
▪ Instructions will be displayed (Appendix F)
 
▪ The shopping list will be displayed and participants will do the shopping task.
 
			
HEALTH AND WEIGHT CONTROL MOTIVES (Qualtrics)	
 
▪ Health and weight control food choice motives will be assessed – questions will be randomised (Appendix G)
 
			

DEBRIEFING (Qualtrics)	
 
▪ Aim guessing in an open-ended response format
 
▪ Insight on the participants' perception of the online shopping task (Appendix H)
 
▪ Text to tell the participants what the study was about (Appendix I)
 

---	--

## 7. STATISTICAL ANALYSIS

All statistical analyses will be performed using SAS version 9.3 (SAS Institute, Inc., 2012 SAS® 9.3. Cary, NC). The level of significance will be set at  $p < 0.05$  for primary and sensitivity analyses and at  $p < 0.01$  for secondary analyses.

### 7.1. Definition of population for analysis

Only participants who have completed the entire study (i.e., baseline assessments + online shopping task + questionnaires) will be included in the analysis. Participants who will have failed at least one attention check or have not complied with the shopping task will be excluded.

Two attention checks will be included:

- In the baseline questionnaire, item 9: This is an attention check. How many times have you visited the planet Mars? Several times / Just once / Never. Correct answer: Never
- In the food choice questionnaire, item 7: This is an attention check. Please choose the answer 2 'Not important'. Correct answer: 2 'Not important'.

We will analyse data from participants who bought at least 5 items out of 10 categories of the shopping list and, if participants buy more than the 10 items requested, as in previous research we will include all items bought [28], [29]. Outcome measures will be based on all the foods in the shopping baskets.

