#### **Health and weight control food choice motives**

Both health and weight control scores will be computed by averaging ratings for individual items of each dimension (health motivation: 6 items; weight control motivation: 4 items). Response options range from 1 to 4: 1 = Not at all important; 2 = A little important; 3 = Moderately important; 4 = Very important. Cronbach’s alpha will be calculated as an indicator of internal consistency in order to compare our data with the original study that developed this measure [27].

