#### 7.4. Missing data

We do not anticipate missing data for analysis of the primary outcome for the population because ED is calculated based on the food database embedded in the online supermarket platform. We do not anticipate missing data either for the dependant variables because the questionnaires will not allow missing answers. Data from participants who start but not finish the study will not be included. Any *a posteriori* withdrawal will be reported and reasons for withdrawal will be documented (e.g., incorrect answers, technical problems).

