#### 7.6. Sensitivity analyses

Sensitivity analyses will be conducted to examine whether the pattern of results from the primary analyses differ after excluding participants guessing the aims of the study.

We will repeat our main analyses with a more stringent criteria for having completed the shopping task as intended (excluding any participants who did not select 10 items in total and 1 item from each category on the shopping list).

We will also repeat the main analysis substituting the composite variable *level of education* by *years in higher education* as a continuous covariate (ANCOVA) and by *highest educational qualification* split into lower vs. higher qualification levels as a binary covariate (2x2x2 ANOVA).

We will report whether sensitivity analyses result in deviations from the pattern of significance to the main analyses (i.e., any significant differences between conditions becoming not significant, and vice versa).

[figure not shown]

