**APPENDIX G: HEALTH AND WEIGHT CONTROL MOTIVES**

**Instruction:** “Several different factors influence our choice of food. Read each item carefully and decide how important the item is to you. There are no right or wrong answers – we are interested in what is important to you”

**It is important to me that the food I eat on a typical day...**

		Not at all important 1	A little important 2	Moderately important 3	Very important 4
Health					
1.	contains a lot of vitamins and minerals				
2.	keeps me healthy				
3.	is nutritious				
4.	is high in protein				
5.	is good for my skin/teeth/hair/nails etc.				
6.	is high in fibre and roughage				
Weight control					
7.	is low in calories				
8.	helps me control my weight				
9.	is low in fat				

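### The second attention check in Section 7.1 gives option 2 a label that is not on the printed response scale, so an attentive participant who follows the words could be excluded

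*Combined protocol and SAP*

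**What the plan says.** Section 7.1 defines the analysis population and lists two attention checks. The second sits in the food choice questionnaire, and its prompt and scoring key read "Please choose the answer 2 'Not important'. Correct answer: 2 'Not important". The same section makes one failure sufficient for removal: "Participants who will have failed at least one attention check or have not complied with the shopping task will be excluded".

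The response scale for that questionnaire is printed twice. Section 7.3, under the food choice motives, begins it as "1 = Not at all important; 2 = A little important", followed by 'Moderately important' for 3 and 'Very important' for 4. The column heading in Appendix G agrees: "A little important 2".

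Section 6 places the questionnaire after randomisation and after the shopping task: "Health and weight control food choice motives will be assessed – questions will be randomised".

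**The concern.** An attention check should separate careful respondents from careless ones. It does this best when the instruction has one plain reading. Here the number is on the scale and the label beside it is not, and the label most resembles a different option. A careful respondent who looks for the words rather than the numeral might settle on option 1.

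What is at stake is entry to the primary analysis. Choosing 1 would be scored as a failure, and a single failure excludes the participant. In that case the check would remove someone who had read the question properly, which is the opposite of its purpose.

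**Working it through.** No figure in the plan is in dispute, so the check is a comparison of wording.

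**1. The printed scale against the check.**

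| Option | Label in Section 7.3 and Appendix G | Named in the Section 7.1 check? |
|---|---|---|
| 1 | Not at all important | Number: no. Words: nearest match, not exact |
| 2 | A little important | Number: yes. Words: no |
| 3 | Moderately important | No |
| 4 | Very important | No |

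Matching on the number gives option 2. Matching on the exact words gives no option. Matching on the closest words gives option 1.

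**2. What follows under the Section 7.1 rule.**
- A participant who follows the number chooses 2, passes, and stays in the analysis.
- A participant who follows the nearest words chooses 1, fails, and is excluded.

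**3. Whether another part of the plan settles it.**
- Appendix G does not show the check; the item numbered 7 there is a weight control item about calories. This is weak evidence about the live survey. Section 7.3 counts 6 + 4 = 10 motive items, while the appendix as reviewed shows nine, so the table may be incomplete. Section 6 also says that the questions are randomised, so the numbering in Section 7.1 need not follow the appendix.
- Section 7.4 promises that any "withdrawal will be reported and reasons for withdrawal will be documented (e.g., incorrect answers, technical problems" and similar causes. A large number of failures might therefore come to light, but counts for each check or each arm are not promised.
- In Section 7.6, one analysis asks whether results "differ after excluding participants guessing the aims of the study", another tightens the definition of a completed task ("We will repeat our main analyses with a more stringent criteria for having completed the shopping task as intended"), and the rest change the education variable. None brings back participants who failed this check.

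**4. Size.** The number wrongly excluded would be the number of attentive participants who reach the item multiplied by the share who follow the words instead of the numeral. The documents give no value for that share, and nothing from which to derive it. Section 7.8 recruits 1,000 to secure at least 788, a margin of 1,000 − 788 = 212, or 212 / 1,000 = 21.2%. The stated allowance of up to about 20% already covers failed attention checks. Adding label failures on top of the full allowance would count the same losses twice, so no shortfall can be derived from the documents.

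**The case against.** The strongest reply is that the number is explicit. Section 7.1 names answer 2 in the prompt and again in the key, and Appendix G prints the numerals beside the labels. A literal reader has one identifiable target, and the data can be scored by number without judgement. This stands. A reader might infer that the check gives two competing instructions that point to two different options. The documents do not support that: the words match no option exactly, and option 1 is only the closest. What is shown is a wrong label on a correctly numbered option.

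A second reply is that the slip may exist only in the text of Section 7.1. This also stands, because the on-screen item is not reproduced. It limits what can be said about consequences but does not remove the inconsistency, since Section 7.1 is the operative definition of the analysis population.

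A third reply is that exclusion after randomisation, once the outcome is recorded, and the lack of a sensitivity analysis restoring excluded participants, apply to any failure of this check, however it is worded. That is right, and neither feature should be counted as a consequence of the label.

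**Conclusion.** The mismatch is certain on the face of the documents, and the rule is wrong as written. Its practical effect is conditional. It requires that the live item carries the Section 7.1 wording and that some attentive participants follow the words over the stated number. The documents establish neither condition.

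A reader might go further and infer that attentive participants will be lost in numbers that bias the comparison or take the trial below its planned power. The documents do not support this. They contain no failure rate, the plan gives the same wording for all arms, and the recruitment margin already allows for failed checks. The number affected is unknown, and no bias or power shortfall is shown. The point is minor, but worth correcting because it lies in a rule that decides who is analysed.

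**What to change.** In Section 7.1, change the label in both the prompt and the key so that answer 2 carries its printed label, 'A little important'. Check that the live survey item shows the same pair. Keep the rule that one failed check excludes. The cost is one label in two places and one look at the survey; the population rule, primary model and sample size do not change.

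Only if data were collected with the mismatched label, two optional additions would help: report failures on this check by arm, and rerun the primary model keeping participants who failed this check and no other criterion. The rerun uses the existing model.

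Two tidying items carry no weight in the conclusion. Printing the check in Appendix G would make the wording verifiable. Section 7.1 also calls the Mars check item 9 where Appendix E numbers it 10; the question and its correct answer are unaffected.
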